9.3 Variables

The investigator collects historic data (demographic and clinical characteristics) from medical records if available, or else by interviewing the patient. Likewise, the investigator collects treatment related data during treatment visits and follow-up visits. The investigator documents the study-relevant data for each patient in the case report form (CRF). The CRF is available upon request (see Table 4: List of stand-alone documents, Annex 1)

Table 2: Tabulated overview on variables collected during the study

Variables	Baseline and first treatment	Further Treatment visits	Follow-up after end of treatment	Long-term follow-up	End of observation
Date of visit	X	X	X	X	X
Patient informed consent	X				
Demography	X				
Vital Signs	X				
Co-morbidities (medical history, concomitant diseases)	X				
Prostate cancer history (initial diagnosis, diagnostic and therapeutic procedures)	X				
WHO pain score	X	X	X		
Performance Status (ECOG)	X	X	X		
Questionnaires BPI-SF and FACT-BP	X	X	X		
Location of bone pain	X	X	X		
Number and location of skeletal lesions (bone scan)*	X	X	X		
Exposure/treatment (dose of Radium-223)	X	X			
Concurrent diagnostic and therapeutic procedures for mCRPC	X	X			
Laboratory parameters including ALP, PSA, blood counts	X	X	X		
Opioid use	X	X	X	X***	
Concomitant medication	X	X			
Adverse Events	X	X	X**		
Symptomatic skeletal events		X	X	X	
Further treatment for mCRPC		X	X	X	
Survival assessment				X	
Reason for end of observation					X

*If available, an additional bone scan together with an assessment of bone uptake of Radium-223 can be documented independently from visits.

**Up to 30 days after last treatment with Radium-223.

***Only opioid use yes/no and date of first use

9.3.1 Variables to determine the primary endpoint(s)

The variables for primary objectives are:

- Pain severity will be measured using the worst pain score of the BPI-SF questionnaire. The BPI-SF will be administered prior to each injection of Radium-223 and, if within routine clinical practice, at a follow-up visit approximately one month after the last injection of Radium-223.

9.3.2 Variables to determine the secondary endpoint(s)

The outcome variables for secondary objectives are:

- Change of pain over time: In addition to pain severity, the subscales of the BPI-SF questionnaire will be evaluated: **The total pain severity subscale** of the BPI-SF is based on the sum of the four items least, worst, average, and current pain. **The pain interference subscale** of the BPI-SF is based on the seven pain interference items.
- Quality of Life: Bone pain related QoL will be measured by evaluation of the total score of the FACT-BP questionnaire. The questionnaire will be filled out together with the BPI-SF prior to each injection of Radium-223 and, if within routine clinical practice, at a follow-up visit approximately one month after the last injection of Radium-223.
- Pain control rate, pain progression rate, and time to first pain progression will be measured using the worst pain score of the BPI-SF questionnaire.
- Evaluation of covariates on pain response:
 - opioid use
 - number of known bone metastases (<6, 6-20, > 20, superscan) at baseline based on the latest bone scintigraphy before the first injection of Radium-223 (not older than 8 weeks)
 - location of bone metastases based on bone scintigraphy
 - level of alkaline phosphatase at baseline (<150 mU/l, 150-300 mU/l, and >300 mU/l)
 - PSA level at baseline (<50 µg/l, 50-200 µg/l, and >200 µg/l)
 - WHO pain score at baseline (WHO-Score 0+1 and WHO-Score 2+3)
 - pretreatment with chemotherapy (yes/no)
 - pretreatment with deep androgen ablation by treatment with abiraterone or enzalutamide (yes/no)
 - bone uptake in known lesions (only faint, higher uptake, and strong uptake compared to surrounding bone)
- location of bone pain
- Radium-223 treatment patterns will be analyzed using dosage, number of treatments and time between treatments
- Course of blood counts

- Treatment-emergent Adverse Events (TEAE) including a description of the event, duration, whether the TEAE was serious, intensity, relationship to Radium-223, action taken, clinical outcome. Patients will be monitored for TEAEs using the NCI-CTCAE Version 4.03.
- Tumor treatment(s) starting after the first application of Radium-223
- Symptomatic skeletal event (SSE) (external beam radiation therapy to relieve skeletal symptoms, new symptomatic pathological vertebral or non-vertebral bone fractures, spinal cord compression, or tumor-related orthopedic surgical intervention)
- Date and cause of death

9.3.3 Demography

For demographic / socio-demographic assessment, the following data will be recorded:

- Year of birth
- Race
- Basic patient characteristics (height, weight)

9.3.4 Co-morbidities (medical history, concomitant diseases)

Any relevant medical finding that was present before start of therapy with Radium-223, independent on whether or not they are still present, has to be documented in the Medical History/Concomitant Diseases section.

9.3.5 Prior and concomitant medication

All medication taken in addition to the product for any indication (either initiated before study start or during the study) is termed concomitant medication.

Information to be collected for medication except for opioid use includes: trade name or INN, start date, stop date/ongoing, total daily dose, unit, and indication.

Opioid use will be documented on a separate form. Information to be collected include trade name or INN, start date, stop date/ongoing, dose, unit, frequency, application route. In addition, the use of pain medication within 24 h of completing the BPI-SF will be collected.

9.3.6 Exposure / treatment

Information to be documented at each Radium-223 administration includes:

- Date
- Number of injection cycle
- Dose
- Unit (kBq/kg)
- Reasons for any significant delay/interruption/discontinuation of treatment

9.3.7 Assessment of therapy

Not applicable

9.3.8 Visits

- Date of visit

9.3.9 Medical History of prostate cancer

Findings meeting the criteria listed below are considered to be relevant to the study indication and have to be documented:

- Prostate cancer classification
 - date of initial diagnosis
 - Gleason score
 - status of primary tumor at study entry
 - progression/relapse
 - date of castration resistance
 - date of initial diagnosis of bone metastases
- prior diagnostic or therapeutic procedures associated with mCRPC
 - surgery/biopsy
 - systemic anti-cancer therapy
 - radiotherapy
 - blood transfusions
- Number of metastases and extent of disease
- Baseline ECOG performance status

9.4 Data sources

The investigator collects historic data (demographic and clinical characteristics) from medical records if available. Likewise, the investigator collects treatment related data, results of tumor assessments and other disease status information, also documented in the medical record, during visits that take place in routine practice. For patient reported outcomes questionnaires filled out by the patient during routine visits are used. For any adverse events that occur, information is directly obtained from the patient. In case a patient is seen by more than one physician for his/her disease (e.g. the patient is monitored by a physician other than the initial investigator), the initial investigator should make every effort to collect information on any visits (including results) that have taken place outside the investigator's site due to the patient's disease, for example by interviewing the respective physician or patient or by obtaining an accompanying letter with detailed information and results.

9.5 Study Size

Aim of the sample size consideration is to assess the precision of the estimate for the pain response rate (the primary outcome) which is defined by the width of the 95% confidence interval with a given sample size. Assuming that at least 70% of patients will be evaluable for the primary analysis of pain response at a post-baseline assessment and 30% to 70% of patients show a pain response, at least 300 patients have to be included to reach a precision of < 20%. In the following table, the different scenarios are shown for actual pain response ranging from 30% to 70%.

Table 3: Width of the 95% CI for the pain response rate, assuming 210 evaluable patients

Actual pain response	Lower Limit of 95% CI	Upper Limit of 95% CI	Width of 95% CI
0.7	0.638	0.762	0.124
0.65	0.585	0.715	0.13
0.6	0.534	0.666	0.132
0.55	0.483	0.617	0.134
0.5	0.432	0.568	0.136
0.45	0.383	0.517	0.134
0.4	0.334	0.466	0.132
0.35	0.285	0.415	0.13
0.3	0.238	0.362	0.124

300 patients is a realistic estimate to be enrolled in a two-year enrollment period, based on current patient numbers and available sites for the treatment. With this sample size and a pain response rate of 65% a precision of < 20 % can be reached assuming subgroups to be at least of 1/2 of this size (i.e. 105 patients). From a clinical point of view, this precision is regarded as meaningful, taking the variance of pain measurements into account.

Calculations were performed with nQuery 7.

The sample size could be increased if the number of patients not evaluable for pain response proves to be higher than the expected 30%.

9.6 Data management

A Contract Research Organization (CRO) will be selected and assigned for EDC system development. The CRF will be part of the EDC system which allows documentation of all outcome variables and covariates by all participating sites in a standardized way. Information on the EDC system is available upon request.

Patient questionnaires will be collected via paper forms which will be entered into the study database by the CRO.

Each patient is identified by a unique central patient identification code. This code is only used for study purposes. The patient code consists of a combination of a country code, site number and patient number. For the duration of the study and afterwards, only the study team is able to identify the patient based on the patient identification code.

The Study Database (SDB) contains all (pseudonymous) study data. The development of this application and the development and setup is done by applying Good Automated Manufacturing Practice (GAMP) standards, fulfilling the FDA 21 CFR Part 11 and EU EudraLex V4 Annex 11 regulations. A set of SOPs and guidelines are used during the study lifecycle project for supporting all study phases from specification, development, study start, deployment and change management and up to study termination.

Detailed information on data management, including procedures for data collection, retrieval and preparation are given in the Data Management Plan (DMP), which is available upon request (see Table 4: List of stand-alone documents, Annex 1).

For information on quality control, refer to section 9.8.

9.7 Data analysis

9.7.1 Statistical considerations

Statistical analyses will be primarily of explorative and descriptive nature.

All statistical details including calculated variables and proposed format and content of tables will be detailed in the Statistical Analysis Plan (SAP). The SAP will be finalized before study database lock. The SAP is available upon request (see Table 4: List of stand-alone documents, Annex 1).

Patients receiving at least one dose of Radium-223 will be considered valid for safety analysis set.

Analyses of pain or QoL will be performed for patients with evaluable patient questionnaires (BPI-SF, FACT-BP, respectively) at baseline and at least one post baseline visit. A clinically increase or decrease in opioid use will be taken into account. E. g. all patients without opioid intake as well as patients taking opioids will be included in analyses until an increase in opioid intake. Further details will be defined in the SAP.

Other analyses will be performed for the safety analysis set unless otherwise defined.

Whenever reasonable, data will be stratified by subgroups (i.e. age, other baseline characteristics).

All therapies documented will be coded using the World Health Organization – Drug Dictionary (WHO-DD). Medical history, any diseases and AEs will be coded using the latest Medical Dictionary for Regulatory Activities (MedDRA) version.

It is planned to have one interim analysis at the time of 6 months after LPFV. This analysis will use uncleaned data and will primarily focus on pain and QoL assessment. The final analysis will be performed after end of the study which is the date the analytical dataset is completely available.

9.7.2 Analysis of demography, disease details, prior and concomitant medication and other baseline data

Demography and baseline characteristics will be described with summary statistics. Concomitant medication will be coded using WHO's drug dictionary.

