Study size	
To reach a precision of < 20% for the primary outcome pain response, 300 patients have to be included, based on the following assumptions: 70% of patients will be evaluable for the primary analysis of pain response at a post-baseline assessment and 30% to 70% of patients show a pain response.
 
300 patients is a realistic estimate to be enrolled in a two-year enrollment period, based on current patient numbers and available sites for the treatment. With this sample size and a pain response rate of 65% a precision of < 20 % can be reached assuming subgroups to be at least of 1/2 of this size.

Data analysis	
Statistical analyses will be primarily of explorative and descriptive nature. Whenever reasonable, data will be stratified by subgroups (i.e. age, other baseline characteristics).
 
Patients receiving at least one dose of Radium-223 will be considered valid for safety analysis set.
 
Analyses of pain or QoL will be performed for patients with evaluable patient questionnaires (BPI-SF, FACT-BP, respectively) at baseline and at least one post baseline visit. The incidence proportion will be provided, along with the exact 95% confidence interval. A clinically increase or decrease in opioid use will be taken into account as will be defined in the SAP.
 
The primary analysis of pain response will be summarized in the population of patients with a score >1 (0="no pain") for the baseline measurement of the 'Worst Pain'-item of the BPI-SF.
 
Pain, including subgroups considered as covariates, and quality of life assessments will be summarized descriptively including mean and change from baseline. An analysis of covariance model will be used to assess changes in pain severity.
 
Time to event variables (TTNT, SSE, OS) will be summarized using Kaplan-Meier estimates. Median event times together with the 25th and 75th percentiles and associated 95% confidence intervals will be presented.
 
All therapies documented will be coded using the World Health

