	
Organization – Drug Dictionary (WHO-DD). Medical history, any diseases and AEs will be coded using the latest Medical Dictionary for Regulatory Activities (MedDRA) version. Incidence of treatment emergent and drug-related AEs will be presented. Additional subcategories will be based on event intensity and relationship to study drug.
 
It is planned to have one interim analysis 6 months after LPFV. This analysis will use uncleaned data and will primarily focus on pain and QoL assessment. The final analysis will be performed after end of the study which is the date the analytical dataset is completely available.

Milestones	
Start of data collection: 01 December 2014
 
End of recruitment: 30 November 2016
 
End of data collection: 31 May 2019
 
Final report of study results: 28 February 2020

5 Amendments

None

6 Milestones

Table 1 presents planned milestones for the project. These milestones are based on a timely review and approval of the project. Administrative changes to milestones due to delays in study preparation and enrollment do not require amendments to the protocol.

Table 1: Milestones

Milestone	Planned date
Start of data collection	01 December 2014
End of recruitment (LPFV)	30 November 2016
Interim analysis	6 months after LPFV (31 May 2017)
End of data collection	31 May 2019
Database cleaned	31 August 2019
Final report of study results	28 February 2020
Registration in the EU PAS register	expected Q4 2014

7 Introduction: Background and Rationale

Prostate cancer is the most common non-cutaneous malignancy in men in Germany. For 2012, 68,260 new cases are estimated (EU: 359,940) and 12,550 died from the disease (EU: 71,020) [1]. The estimated age-standardized rate for prostate cancer incidence in Germany is 114.1 per 100,000 (EU: 110.8) [1]. Incidence rates increase sharply beyond the age of 50 years. For men aged 50-54 years, the incidence rate is 82 per 100,000 men; ten years later, at age 60-64 years, the rate is more than five times higher at 432 per 100,000, and at 70-74 years the rate is almost nine times higher at 722 per 100,000 [2]. Based on our growing and aging population, it is expected that by the year 2030, the burden of prostate cancer will increase to approximately 89,000 new cases and 17,000 new deaths in Germany (EU: 485,000 and 103,000, respectively) [3].

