Annex 1: List of stand-alone documents

Table 4: List of stand-alone documents

Number	Document Name / Reference number	Date	Title
1	XF1412_List_of_active_physicians final	Will be available at end of recruitment	List of all active physicians
2	XF1412_CRF	tbd	CRF
3	XF1412_DMP	Will be available at time ready to enroll	Data Management Plan
4	XF1412_SAP	Will be available before study database lock	Statistical Analysis Plan
5	XF1412_QRP	Will be available at time ready to enroll	Quality Review Plan

* Draft versions are indicated by date and <draft> in brackets. “tbd” indicates documents that are not available at the time of protocol creation, but will be issued at a later stage.

**Annex 2: ENCePP checklist for study protocols****ENCePP Checklist for Study Protocols** (Revision 2, amended)**Study title:**

PARABO - Pain evaluation in Radium-223 (Xofigo®) treated mCRPC patients with bone metastases – a non-interventional study in nuclear medicine centers

Study reference number:

Section 1: Milestones	Yes	No	N/A	Page Number(s)

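### The SAP is due only before database lock, 24 to 27 months after an interim that can already show nearly all primary-endpoint data, while the opioid rule and the headline estimate are still open

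*Protocol*

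**What the plan says.** **SAP deadline.** Section 9.7.1 says: "The SAP will be finalized before study database lock". Annex 1, Table 4 repeats this for the SAP: "Will be available before study database lock". In the same table the data management plan and the quality review plan are due by the time sites are ready to enrol.

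**Interim.** Section 9.7.1 and Table 1 (Section 6) plan one interim analysis six months after the last patient's first visit, dated 31 May 2017. Section 9.7.1 adds: "This analysis will use uncleaned data and will primarily focus on pain and QoL assessment". Table 1 puts end of recruitment at "30 November 2016", end of data collection at 31 May 2019 and the cleaned database at "31 August 2019". It lists no lock date.

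**Already fixed.** Sections 9.1.1 and 9.7.4 define response as a two-point fall in BPI-SF worst pain from baseline at any later assessment. Section 9.7.1 requires a usable questionnaire at baseline and at least one later visit. Section 9.7.4 restricts the primary analysis to baseline scores above 1.

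**Left open.**
- Opioids. Section 9.7.1 says "A clinically increase or decrease in opioid use will be taken into account" and, purely as an example, keeps patients in the analysis until their opioid intake rises. The Abstract (Section 4) has "opioid use will be taken into account as will be defined in the SAP".
- Headline figure. Section 9.7.4 asks for a proportion with an exact 95% interval at each assessment after baseline, but defines response over any of them. It does not say which proportion is the primary estimate.

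**The concern.** Leaving detail to an SAP is normal and is not the complaint. The difficulty is the date the protocol sets for the SAP relative to its own interim. The interim is about pain, which is the primary endpoint, and pain questionnaires stop about a month after the last injection. The two further years of follow-up add survival, skeletal events, later treatment and first opioid use, but no BPI-SF data. The interim can therefore show the pain result almost in full while the rules that complete the primary analysis need not yet exist.

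With no comparator, the response rate and its interval are the finding. If the coding of opioid escalation and the choice of headline proportion can be made after the rate has been seen, a reader of the final report cannot tell whether they were chosen blind to it.

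**Working it through.** **1. The plan's own figures.** Evaluable patients: 300 x 0.70 = 210. At 65% response the half-width is 1.96 x sqrt(0.65 x 0.35 / 210) = 0.0645, with limits 0.585 and 0.715. Table 3 (Section 9.5) gives the same limits and a width of 0.13, so a half-width of about 6.5 points. Six months after 30 November 2016 agrees with the stated 31 May 2017.

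**2. When the last primary-endpoint data arise.** Inputs:
- last enrolment on 30 November 2016 (Table 1);
- typical four-week interval (Section 9.2.7);
- BPI-SF before each injection and, where routine, about one month after the last (Section 9.3.1);
- six injections, an assumption, because Section 7 gives that number only for the phase III trial.

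Sixth injection: 30 November 2016 + 5 x 28 days = 19 April 2017. Last questionnaire: + 30 days = 19 May 2017. That is 12 days before the interim. Fewer injections would bring it forward.

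**3. Sensitivity to delay.** The full pain window is 140 + 30 = 170 days. From last enrolment to the interim is 182 days. Assume uniform accrual over the 730 days from 1 December 2014 to 30 November 2016, and an extra D days per patient for postponed injections or data entry. The share of patients with a complete window is then 1 - max(0, 170 + D - 182) / 730. Applying the same calculation to each of the six scheduled post-baseline assessments gives the last column.

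| D (days) | Patients with complete window | Scheduled post-baseline BPI-SF assessments in |
|---|---|---|
| 0 | 100% | 100% |
| 28 | 97.8% | 99.6% |
| 56 | 94.0% | 98.7% |
| 84 | 90.1% | 97.1% |

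**4. Gap to the SAP deadline.** From 31 May 2017 to the end of data collection (31 May 2019) is 24 months. To the cleaned database (31 August 2019), the nearest stated stand-in for lock, it is 27 months.

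**5. What the open opioid rule can do.** The documents give no escalation rate, so these inputs are assumptions: a share e of evaluable patients escalates, a share r of those would otherwise count as responders, and the overall rate is 65%. Coding every escalator as a non-responder lowers the rate by e x r.

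| e | r | Loss (points) | Resulting rate |
|---|---|---|---|
| 10% | 30% | 3.0 | 62.0% |
| 10% | 65% | 6.5 | 58.5% |
| 20% | 30% | 6.0 | 59.0% |
| 20% | 65% | 13.0 | 52.0% |

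The range is 3 to 13 points against a half-width of 6.5. It supposes that all responses of escalators are cancelled. If responses before escalation still count, as the example in Section 9.7.1 suggests, the loss is smaller.

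**The case against.** The strongest reply is that little is truly open and little depends on it.

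- **The endpoint is largely specified.** A reader might infer that pre-specification of the primary endpoint is lost. The protocol does not support that: the two-point threshold, the any-assessment definition, basic evaluability and the baseline restriction are all stated, and the opioid rule has a direction by example. This stands, and it narrows the point to the two open items.
- **Censoring rules.** Section 9.7.5 defers these to the SAP too, but for time to next treatment, skeletal events and survival. They do not touch the binary primary endpoint.
- **Size.** It is tempting to say that each open rule could move the rate by more than its confidence interval. Only the opioid rule has been quantified, on assumed inputs. Two of its four scenarios fall inside the half-width, one about equals it, and the largest about equals the full width of 0.13.
- **Status of the interim.** Calling it the primary analysis is inference. Section 9.7.1 places the final analysis after the end of study, visit dates are not fixed, the last questionnaire is collected only if routine, and paper forms have to be entered. Those reservations are fair, but step 3 shows that nearly all the data are still in with delays of up to 84 days.
- **Consequence.** The analysis is exploratory and descriptive, the ENCePP checklist marks formal hypotheses as not applicable, and no stopping decision hangs on the interim. No type I error is spent.
- **Before lock is a latest date.** The sponsor may finish the SAP sooner, so nothing shows an intention to write rules after the interim. That is correct, but nothing in the protocol requires it earlier either.

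**Conclusion.** The point holds in limited form. The only SAP deadline in the protocol falls 24 to 27 months after a pain-focused interim by which, with six four-weekly injections, about 90 to 100% of patients would have a complete pain window for delays of 0 to 84 days.

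Two elements of the primary analysis can be decided in that interval: what counts as a clinically relevant opioid change and how a patient is classified after escalation, and which proportion is the headline estimate. On the stated assumptions the first alone is worth about 3 to 13 points on a 65% rate, so it may be smaller or larger than the planned half-width of about 6.5.

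The dates are firm, apart from the missing lock date. The number of injections and the escalation inputs are assumptions. The risk is a data-driven choice of the reported rate in an open single-arm study. It is of moderate importance and is neither an error-rate problem nor evidence of intent.

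**What to change.** Change Section 9.7.1 and the SAP row of Table 4 to the effect that *the SAP, including the opioid rule for the pain analyses and the single primary estimate, is final before the data cut for the interim analysis, and any later change is labelled as made after the interim.* The opioid rule should state what size of change counts and whether a patient who escalates is a non-responder, contributes only assessments before the increase, or leaves the denominator. The primary estimate should be named as either the any-assessment proportion or the proportion at one stated assessment.

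The cost is earlier SAP writing; no patients, visits or procedures are added. Cleaning the pain and opioid forms for the interim cut is a separate option. It would change the sponsor's stated use of uncleaned data and need an extra query round, and the main fix does not depend on it.
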